- 1. Primary outcome: The group treated with MSA adjunctive to ADT will show a greater mean change from baseline to endpoint in total score as compared to the group treated with placebo (PBO) adjunctive to ADT as measured by the
 - a. Massachusetts General Hospital Cognitive-Physical Function Questionnaire (MGH-CPFQ)
- 2. Secondary outcome:
 - a. MSA adjunctive to ADT will demonstrate clinically acceptable safety and tolerability, compared to placebo, based on
 - i. spontaneously reported adverse events and significant adverse events
 - ii. significant changes in blood pressure and pulse
 - iii. significant changes in weight
 - iv. significant changes in electrocardiogram
 - v. significant changes in the Rush Sexual Inventory
 - b. The group treated with MSA adjunctive to ADT will show a greater mean change from baseline to endpoint as compared to the group treated with PBO adjunctive to ADT as measured by the change on
 - i. MGH-CPFQ individual item analysis
 - ii. MADRS scores:
 - 1. Total score
 - 2. Subscales
 - 3. Individual item analysis
 - 4. Percent of "responders" (\geq 50% reduction in score baseline to endpoint)
 - 5. Percent reaching "remission" (score of ≤ 10 at endpoint)

- c. The group treated with MSA adjunctive to ADT will show statistically significant improvement in core residual symptoms of MDD extant on monotherapy ADT as measured by the
 - i. PGI (Patient Impression and Improvement) scales
 - ii. Quick Inventory of Depressive Symptomatology-16 (QIDS-16) total score (≤ 6) and subscale
 - iii. Clinical Global Impression-Severity (CGI-S); and, Clinical Global Impression-Improvement (CGI-I)
 - iv. QIDS total score and subscale
- d. The group treated with MSA adjunctive to ADT will show statistically significantly improvement in overall functioning (work, social and cognitive) when compared to the group treated with PBO and ADT as measured by the
 - i. Total and individual item scores from the HDRS-17 and -28
 - ii. Maier and other subscale scores from the HDRS-17 and -28
 - iii. Scale For Assessment Of Negative Symptoms (SANS)
 - iv. Health Status Questionnaire, 2nd ed. (HSQ 2.0)
 - v. SF-36 Health Survey (SF36)
 - vi. Fawcett Experienced Pleasure Index (EPI)
 - vii. Endicott Work Productivity Scale (EWPS)
 - viii. Sheehan Disability Scale (SDS)
 - ix. Fatigue Associated with Symptoms of Depression (FASD)

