- **Study Design:** A randomized, double-blind, placebo-controlled, parallel-group study of flexible dose mixed salts amphetamine (5-60 mg) adjunctive to antidepressant therapy among adult outpatients with major depressive disorder responding inadequately to current antidepressant therapy.

Fig. 1: Treatment Groups

Visit	Phase	Weeks	Group	Group	Procedures
		on med	1	2	
V1		Scr			Inclusion/Exclusion
V2		0			Baseline measurement + disp.
V3	Ι	1	MSA	PBO	Measure effect of 1 week on study med + disp.
V4	Ι	2	MSA	PBO	Measure effect of 2 weeks on study med + disp.
V5	Ι	3	MSA	PBO	Measure effect of 3 weeks on study med + disp.
V6	II	4	MSA	MSA	Measure effect of 3 weeks on study med + disp.
V7	II	5	MSA	MSA	Measure effect of 3 weeks on study med + disp.
V8	II	6	MSA	MSA	Measure effect of 3 weeks on study med
V9		(8)			Safety follow-up

Fig. 2: Study Design Overview

The treatment phase of the study consists of 2 phases (21 treatment days per phase). Study Phase 1 will consist of visits 2 (baseline) through 5. Study Phase 2 will consist of visits 6 through 8. There will be a follow-up visit 2 weeks following visit 8. There is a one-week interval between study visits, with a scheduling window of \pm 3 days allowed.

Mixed salts amphetamine is FDA-approved for Attention Deficit-Hyperactivity Disorder (ADHD) and superior in efficacy to placebo; therefore, comorbid ADHD will be statistically controlled as a continuously-variable covariate, but will not be considered an exclusionary condition.

The primary analysis will be a repeated measures analysis of variance using a mixed-effects model (PROC MIXED-MMRM). The primary outcome measure will be the MGH-CPFQ total score at baseline and the MGH-CPFQ total score at the end of the trial. The independent variables will be the study visit, the treatment in the previous phase, and treatment assignment. The variance covariance matrix for the repeated measures will be unspecified.

Enrollment Period: The enrollment period is estimated to be 6 months. The last patient is expected to complete the study by March 31, 2010.

Number of Subjects: 40 subjects will be randomized (20 to each treatment arm). Additional subjects may be consented to allow for screen failures. Subjects who terminate early post-randomization will be replaced only sufficiently to ensure a total number of 24 (12 to each treatment arm) evaluable subjects.

Duration of Subjects' Study Participation: There will be a total of 9 study visits over a period of 9 weeks.

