Study Assessments and Primary Endpoints: The difference in absolute change in score from baseline to endpoint in the MGH-CPFQ between the MSA and the PBO groups is the primary endpoint. Key secondary endpoints will be difference in absolute change from baseline in MADRS score between MSA and PBO, difference in remission rates (MADRS < 11) between MSA and PBO, the change from baseline in total score at endpoint of MGH-CPFQ item analysis, difference in change scores on the CGI-S, CGI-I and QIDS. Safety outcome measures: adverse events, physical examinations, vital signs; blood pressure, orthostatic; EKG; Rush Sexual Inventory (RSI).

Statistical Methods: The randomized sample includes all patients who are randomized. The Safety sample will include those randomized patients who received at least one dose of doubleblind study medication as indicated on the dosing record. The efficacy sample will include those patients in the safety sample who have at least one efficacy evaluation post-randomization. The last observation carried forward (LOCF) data set includes data recorded at a given visit after randomization, or, if no observation is recorded at that visit, data carried forward from the previous postrandomization visit. The LOCF data set is primary, and analysis of the observed case data set also will be conducted.

The primary analysis will compare pooled MGH-CPFQ response rates between PBO and MSA and PBO non-responders. Differences in response rates will be compared using the CMH General Association Test. Descriptive statistics on non-primary groups will be conducted.

This study seeks to estimate the strength of any statistically significant relationship, or effect size, in addition to statistical significance of found treatment effects.

Secondary Endpoints Analysis: Differences in remission (defined as an endpoint MADRS score <11) rates will be compared using the CMH General Association Test. Logistic regression analysis will be performed to explore the relationship between response and patients' demographics and prognostic variables including baseline QIDS score, gender, site, and age, etc. Similar analyses will be performed for remission.

Fig. 3	: Stud	y Proce	dures	Table
--------	--------	---------	-------	-------

			Treatment period 1			Treatment period 2			
Study Visit	V1 Screen	V2 Baseline	V3	V4	V5	V6	V7	V8	V9 F/UP
End of Week	-1	0	1	2	3	4	5	6	8
Day	-7	0	7	14	21	28	35	42	56
Informed consent	Х								
Demographic data	Х								

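### Predictors of response and remission are explored only through cut scores; adding a linear model of the continuous totals would recover power at no data cost

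*Combined protocol and SAP*

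**What the plan says.** The Statistical Analysis section, under Secondary Endpoints Analysis, gives one method for the predictor question: "Logistic regression analysis will be performed to explore the relationship between response and patients' demographics and prognostic variables including baseline QIDS score, gender, site, and". The named list ends with age and is left open. The section then adds "Similar analyses will be performed for remission".

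Both outcomes are binary. The plan describes "remission (defined as an endpoint MADRS score <11". The only response cut that it states is a fall of at least half in MADRS score (Research Hypotheses, 2b). Statistical Methods also speaks of MGH-CPFQ response rates, but no cut is given for that scale.

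The Study Procedures Table (Fig. 3) has the MADRS and the MGH-CPFQ completed at every visit from V2 to V8. Continuous change is used to compare the arms: it is the primary endpoint, the key secondary MADRS endpoint and the outcome of the mixed model under Study Design. No predictor model on a continuous score is described.

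On size, Number of Subjects states "40 subjects will be randomized (20 to each treatment arm" and limits replacement of early terminators to what is needed "to ensure a total number of 24 (12 to each treatment arm) evaluable subjects".

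**The concern.** Cutting a score at a threshold discards how far each subject lies from it. In a trial of 40 that loss is large relative to the information available. The predictor list has four named entries and is open-ended, so a logistic model that takes them together would have few events per term. The plan sets no limit on predictors and has no rule for separation (a predictor, or a combination of them, that splits events from non-events perfectly, so that estimates do not exist).

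At stake is whether a real association with age, gender or baseline severity would be seen, and whether the reported odds ratios would be stable. The plan also says that it wants effect sizes as well as significance, and coefficients on a continuous scale serve that aim better.

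**Working it through.** The plan states no power, alpha, predictor effect or expected response rate, so it has no figure to reproduce. The check compares the two models under declared assumptions.

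**Inputs from the documents.** 40 randomised 1:1; floor of 24 evaluable; predictors baseline QIDS, gender, site, age; remission at MADRS below 11. Background remission figures of 11% to 33% are cited in the introduction, but not as planning rates.

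**Assumptions.** Two-sided 5%; normal score; correlation ρ of 0.3-0.5 between one predictor and the score; treatment effect 0.5 SD; event rate 30-50%; model terms treatment, baseline severity, age and gender.

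**1. Events per named predictor** (n × rate ÷ 4).
- 22% rate: 24 × 0.22 ÷ 4 = 1.3; 40 × 0.22 ÷ 4 = 2.2.
- 33% rate: 24 × 0.33 ÷ 4 = 2.0; 40 × 0.33 ÷ 4 = 3.3.

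**2. Hand check of the cut.** Take a balanced two-level factor, 20 v 20, with a standardised difference of 0.8.
- Continuous: Φ(0.8 × √10 − 1.96) = Φ(0.57) = 71.6%.
- Cut midway: proportions Φ(0.4) = 0.655 and Φ(−0.4) = 0.345, difference 0.31. The null SE is √(2 × 0.25 ÷ 20) = 0.158, and 1.96 × 0.158 = 0.31, so power is about 50%.
- Loss: about 21 points, rising to 28 with less central cuts (power 44%).

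**3. Simulation.** Score = ρ × predictor + 0.5 × (treatment − 0.5) + error, cut to give the event rate, 2,000 runs per setting. The linear and logistic models have the same four terms. Power (%) for a predictor with ρ = 0.4:

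| n | Event rate | Linear | Logistic, Wald | Logistic, LR | Loss, Wald | Loss, LR |
|---|---|---|---|---|---|---|
| 40 | 30% | 68.6 | 42.1 | 51.1 | 26.5 | 17.5 |
| 40 | 50% | 69.8 | 46.1 | 54.8 | 23.7 | 15.0 |
| 24 | 30% | 44.5 | 13.2 | 33.0 | 31.3 | 11.5 |
| 24 | 50% | 44.4 | 20.7 | 38.0 | 23.7 | 6.4 |

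Over ρ = 0.3-0.5 at n = 40 the Wald loss is about 10-28 points. A separate simulation at event rates of 35-50% gave 13-26 points (Wald) and 7-18 (likelihood ratio). At a 25% rate it gave 17-37 and 11-24.

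**4. Test level.** With no true association, the likelihood-ratio test rejected in 6.6-8.3% of runs at n = 40 and 8.5-10.5% at n = 24. The linear model rejected in 4.7-5.6%. Part of the likelihood-ratio test's apparent power is therefore excess false positives.

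**5. Adding the scale's own baseline.** With five terms at n = 40, effect 0.4 and event rates of 30-50%:
- Age, or a QIDS uncorrelated with that baseline: 68-71% linear, against 41-47% (Wald) or 49-55% (likelihood ratio).
- QIDS correlated 0.7 with that baseline (assumed): 42% linear, against 24-29% or 32-35%.

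**6. Separation** (share of trials, predictors fitted jointly).

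| Event rate | n = 24 | n = 40 |
|---|---|---|
| 33-50% | 1-13% | under 1% |
| about 31% | 6-12% | under 1% |
| 25% | 9-27% | 2-7% (rates 20-25%) |
| 20.5-22% | 17-37% | 2-7% (rates 20-25%) |
| 15% | 34-61% | 10-23% |
| 11% | 51-75% | 24-41% |

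**The case against.** **The analysis is exploratory and the outcomes are legitimate.** Both are true. The introduction treats sustained remission as the accepted goal and describes the conventional cut, so asking what predicts remission is reasonable. This is why the binary models should stay. It does not explain why the continuous totals go unused for the same question.

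**The joint model with a treatment term is assumed.** Correct: the plan does not say how predictors enter. Fitted one at a time at n = 24 and 30% events, separation was under 0.1% for a continuous predictor and about 1% for gender. The separation figures above apply only to joint fitting. Only one institution's review board is named; if there is a single site, that term drops out and separation falls to the lower end of each range.

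**Change and remission are different questions.** Under one illustrative set of assumptions (baseline 26, SD 5; improvement 12, residual SD 7), a higher baseline correlates +0.14 to +0.39 with improvement but −0.21 to −0.39 with remission. That stands for the scale's own baseline. For the other predictors, change is a difference between baseline and endpoint; once baseline is in the model, change and endpoint score give the same coefficient apart from sign.

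**Baseline QIDS overlaps with baseline MADRS.** This stands as a limit on what can be learnt about QIDS. It lowers power in both models, and the linear model keeps its advantage (step 5).

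**The size of the loss depends on the assumptions.** It does. Widening them (weak predictors, or rates down to 15%) moves the loss from about 2 points to nearly 60.

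**Conclusion.** The point holds as a low-cost improvement. For moderate predictors (ρ 0.3-0.5), n = 40, event rates of 30-50% and identical terms in both models, using only cut scores costs about 10-28 points of power by Wald test. The likelihood-ratio loss is smaller, with type I error of about 7-8%. None of these figures can be derived from the plan alone.

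Three stronger readings might be inferred, and the documents do not support them:

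- *That the logistic models will often be impossible to fit at n = 24.* At event rates of 30-50% even joint fitting fails in a small minority of trials (about 1-14%). The figure of 24 is only a replacement floor. The efficacy sample takes dosed subjects with any post-randomisation efficacy evaluation, with LOCF primary, so it should sit nearer 40. Separation is a concern mainly at rates of about 25% or lower, or if n falls near 24.
- *That the treatment comparisons are weakened.* They have their own continuous endpoints; only exploratory predictor findings are affected.
- *That the trial sets out to show which inadequate responders benefit.* The stated objective is efficacy, safety and tolerability, and no predictor hypothesis is listed. That question would need treatment-by-predictor interactions, which are not planned.

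**What to change.** In Secondary Endpoints Analysis, add as the main exploratory predictor analysis:

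- a linear model of MGH-CPFQ total and another of MADRS total at the placebo-controlled endpoint (by the design table, the end of Phase 1 at Visit 5);
- adjusted for treatment and the same scale's baseline, with age, gender and baseline QIDS as a closed predictor list;
- coefficients reported with 95% CIs, and a note that QIDS overlaps with the MADRS baseline.

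Keep the response and remission models as supplementary, with few predictors and Firth-penalised logistic regression. State which response is meant, and give the cut if it is MGH-CPFQ response.

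The cost is one paragraph of wording and no new data. The small downside is that the main coefficients are in scale points rather than odds of remission, which clinicians may find less direct.

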- Upon a subject's completion of the study (visit 8), in order to facilitate continuation of care by a non-study clinician

Monitoring of Study/Oversight:

Study staff will monitor source data and case report forms by regular internal monitoring. .

IRB Review/Ethical Conduct of Study:

IRB Review: Prior to enrolling any subjects, documentation will be obtained that the study protocol and informed consent form have been approved by the Rush University Medical Center Institutional Review Board. Any change in the protocol or informed consent form will require prior written approval except to prevent injury or risk to a subject.

Regulatory Considerations: This study will be conducted in accordance with the ethical principles stated in the most recent version of the Declaration of Helsinki or the applicable guidelines on good clinical practice, whichever represents the greater protection of the individual.

Informed Consent: The informed consent document, in conjunction with verbal discussion of the protocol, will be used to explain the study, including the risks and benefits, to the subject in simple terms before the subject is entered into the study. The investigator is responsible to see that informed consent is obtained from each subject and to obtain the appropriate signatures and dates on the informed consent document prior to the performance of any protocol procedures and prior to any changes made to a subject's medical treatment plan for the purpose of study participation. The original signed consent form will be retained by the investigator.

Confidentiality:

All information collected about subjects for the purposes of this study will be treated as confidential to the extent allowed by law. The information obtained while subjects are enrolled in this study, including all study-related hospital and office records, will be made available to the study doctor, Bristol-Myers Squibb, the Institutional Review Board and other regulatory agencies, including the United States Food and Drug Administration (U.S. FDA).

Intended Use of Data:

The results of this research project may be presented at meetings or in publications, but the identity of subjects will not be disclosed in such presentations.

Statistical Analysis:

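### The MADRS remission comparison uses no baseline covariate although baseline MADRS is collected; at 12 to 20 per arm this leaves precision unused and chance imbalance in the estimate

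*Combined protocol and SAP*

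**What the plan says.** In Statistical Analysis, the Secondary Endpoints Analysis paragraph defines the outcome and the test: "Differences in remission (defined as an endpoint MADRS score <11", and these "rates will be compared using the CMH General Association Test". No stratification factor or covariate is given. Research Hypotheses, item 2.b, gives the cut-off as 10 or below, which is the same rule for whole-number scores.

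The same paragraph then says "Logistic regression analysis will be performed to explore the relationship between response and patients' demographics". Its list of further covariates reads "prognostic variables including baseline QIDS score, gender, site, and age, etc", followed by "Similar analyses will be performed for remission". The covariate list is open-ended and names no treatment term.

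Other relevant places:
- Fig. 3 schedules MADRS at every visit from V2 (baseline) to V8.
- Inclusion criterion 4 sets severity at entry by HDRS-17, not MADRS.
- Randomisation is by blocks, and no stratification by severity is stated.
- Number of Subjects gives 40 randomised (20 per arm) and a floor of 24 evaluable (12 per arm).
- The one covariate named for adjustment anywhere is comorbid ADHD (Study Design), without saying which analysis of which outcome it belongs to.
- The number of sites is not stated. The protocol and consent form must "have been approved by the Rush University Medical Center Institutional Review Board", and the text refers to a single research center.

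**The concern.** Remission is a fixed cut-off on the endpoint score, so a subject who starts lower on MADRS is more likely to finish below 11 whatever the treatment. Entry on a different scale and randomisation without a severity stratum leave baseline MADRS free to differ between small arms. An unstratified CMH test on a 2x2 table is Pearson's chi-square times (N-1)/N, so nothing in it uses the baseline value. The severity covariate named in the exploratory model is QIDS, a different scale completed by the patient.

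The estimate for a key secondary endpoint is at stake. The plan says it wants effect size as well as significance, and in an unlucky draw part of the observed remission difference would be starting severity.

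**Working it through.** The documents give no alpha, power, SD, remission rate or baseline-endpoint correlation, so there is no planned figure to reproduce. Assumed below: two-sided 5% level; 20% remission on placebo; correlation r between baseline and endpoint MADRS of 0.3 to 0.7; and, for power, a shift of 0.9 SD on the underlying score (remission about 20% against 52%).

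**1. How likely is a sizeable imbalance?** The SD of the standardised baseline difference is sqrt(2/n).
- n = 20: sqrt(2/20) = 0.316. P(imbalance above 0.5 SD, either direction) = 2 x [1 - Phi(0.5/0.316)] = 11.4%.
- n = 12: sqrt(2/12) = 0.408. P = 2 x [1 - Phi(0.5/0.408)] = 22.1%.

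Half of each figure is imbalance in favour of MSA.

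**2. What does it do to the remission difference?** Given an imbalance above 0.5 SD in favour of MSA and no true effect, the mean observed difference in 4,000 simulated trials per setting was:

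| r | 20 per arm | 12 per arm |
|---|---|---|
| 0.3 | +4.0 points | +6.5 points |
| 0.5 | +8.3 points | +9.6 points |
| 0.7 | +12.5 points | +12.6 points |

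A hand check at 20 per arm: the mean imbalance given that it exceeds 0.5 SD is 0.316 x phi(1.58)/[1 - Phi(1.58)] = 0.635 SD. Multiplying by r and by the normal density at the 20% point (0.280) gives 0.635 x 0.5 x 0.280 = 0.089, or about 9 points at r = 0.5, in line with the simulation.

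**3. Is the planned test valid?** Yes. Over all randomisations the mean difference under no effect was within 0.6 points of zero. CMH type I error was 0.045 to 0.050 (20 per arm) and 0.035 to 0.044 (12 per arm).

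**4. Does ordinary logistic adjustment work?** Not at this size. With arm and baseline MADRS, the likelihood-ratio test rejected under no effect in 0.067 to 0.080 of trials (20 per arm) and 0.088 to 0.110 (12 per arm), against a nominal 0.05.

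**5. Does a penalised model work?** Firth logistic regression with the same two terms (penalised likelihood-ratio test, 2,000 trials per setting) had type I error 0.044 to 0.052 (20 per arm) and 0.037 to 0.043 (12 per arm). Power, CMH then Firth:

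| r | 20 per arm | 12 per arm |
|---|---|---|
| 0.3 | 0.59, 0.58 | 0.41, 0.39 |
| 0.5 | 0.60, 0.64 | 0.38, 0.38 |
| 0.7 | 0.60, 0.72 | 0.40, 0.46 |

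The SD of the estimated risk difference fell in every setting. At 20 per arm and r = 0.5 it went from 0.149 to 0.129, a cut of (0.149 - 0.129)/0.149 = 13%. The estimate shrank by about 1 to 3 points.

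**6. Why only two terms?** At 20% to 40% overall remission there are 40 x 0.2 = 8 to 40 x 0.4 = 16 remitters, or 24 x 0.2 = 4.8 to 24 x 0.4 = 9.6 at the evaluable floor. Four terms (arm, QIDS, sex, age) would leave 2 to 4 remitters per term among 40, and 1.2 to 2.4 among 24.

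**7. The site term.** In a simulated data set of 40, a constant site column made the design rank 5 of 6. The treatment coefficient was 0.592 (SE 0.717) with and without it, and the fitted values were the same.

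**The case against.** The strongest defence is that nothing is broken. The CMH test already allows for chance imbalance in its sampling error, which is large. At 25% remission, 1.96 x sqrt(2 x 0.25 x 0.75/n) is about 27 points at 20 per arm and 35 at 12. The median absolute imbalance, with r = 0.5, moves the difference only 0.674 x 0.316 x 0.5 x 0.318 = 3.4 points (20 per arm), or 4.4 points with 0.408 in place of 0.316 (12 per arm). The power gain from adjustment is nil to slightly negative when the correlation is low or only 12 per arm are evaluable. All of this stands, and it limits the point to precision and to the estimate conditional on the draw obtained. It does not remove the point, because the baseline value is already collected. The separate endpoint, "difference in absolute change from baseline in MADRS score between MSA and PBO", does not repair the remission estimate.

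Four stronger readings are tempting but not supported:
- **The logistic model cannot be fitted because site is constant.** A single centre is a fair inference from the one IRB, but the documents do not state it. Even then the column is aliased with the intercept and drops out, so it is redundant and does not prevent a fit.
- **The logistic model is a faulty treatment comparison because it omits arm and baseline MADRS.** It is described as exploratory, its list does not exclude baseline MADRS, and the text does not say that all predictors enter one model.
- **The distortion is typically 10 to 13 points.** With r = 0.5 and 25% remission, those figures arise at the 95% limits of imbalance (1.96 x 0.316 = 0.62 SD and 1.96 x 0.408 = 0.80 SD). They are not typical.
- **The same argument covers MADRS response.** Response is a reduction of at least 50% from baseline, not a fixed cut-off, and the Statistical Analysis section names no test for it.

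**Conclusion.** The point holds as a matter of efficiency and of conditional error in the estimate, not of validity. As written, the treatment comparison for MADRS remission ignores a baseline value of the same scale that is collected at V2. There is an 11% (20 per arm) to 22% (12 per arm) chance of an imbalance above 0.5 SD in one direction or the other. If it favours MSA, it carries about 4 to 13 points into the remission difference at 20 per arm. The probabilities follow from the sample size alone. The shifts, power and precision figures rest on assumed correlations, remission rates and alpha, because the documents give none. The change is worth making for a key secondary endpoint, with modest expectations about power.

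**What to change.** In Secondary Endpoints Analysis, make the remission comparison a Firth-penalised logistic model (or another small-sample method, such as an exact or permutation test that uses baseline) with treatment arm and V2 MADRS only. Report the standardised risk difference with its 95% CI. Keep the CMH test as a sensitivity check. Do not use an ordinary likelihood-ratio logistic test.

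Minor wording in the same paragraph: add baseline MADRS to the exploratory remission model, close the covariate list, and delete site if the trial has one centre (otherwise state the number of sites).

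The visit that counts as endpoint for remission also has to be stated, because both groups receive MSA in Phase 2. That is a separate question, and covariate adjustment does not settle it.

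The cost is a few sentences and a few lines of program, with no new data. The statistical price is slight shrinkage of the estimate (about 1 to 3 points in the simulations) and little or no power gain if the baseline-endpoint correlation is low or only 12 per arm are evaluable.
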